5.1.3 The effect of food on PK of DZD9008

An additional cohort ($n = \sim 10$) in Part A will be enrolled at the defined dose (i.e. predicted efficacious dose, RP2D, etc) to evaluate food effect on PK of DZD9008.

Figure 2 Study plan of food effect cohort

Note: ~10 patients are planned to be enrolled

* The washout time of each treatment period might be updated in light of emerging human PK data. In general, after single dose, at least 7 days or 5 x half-lives will be allowed for drug elimination.

This is a food effect cohort following cross-over study design. Patients in this cohort will firstly be randomized to receive a single dose of DZD9008 under either fasted or fed condition (a high fat meal), with 5 patients in each condition. After a 7-day washout period or 5 x half-lives (whichever is longer), these patients will be switched to receive a single dose of DZD9008 under cross-over condition. Blood samples will be taken in both conditions at defined time points for the assessment of DZD9008 plasma concentrations.

Fasted condition: Patients must fast for ≥ 1 hours prior to taking a dose and to ≥ 2 hour post dose.

Fed condition: Patients should start ingestion of a recommended meal 30 minutes prior to administration of DZD9008. Patients should finish this meal within 30 minutes or less; however, DZD9008 should be administered at 30 minutes after start of high fat meal. DZD9008 should be administered with 240 mL (8 fluid ounces) of water. No food should be allowed for at least 2 hours post-dosing.

Water will be restricted from 1 hour pre-dose until 1 hour post dose, except for the water administered with DZD9008, and any drink provided as part of the meal in the fed portion of the study.

Patients should receive standardized meals. A high-fat (approximately 50 percent of total caloric content of the meal) and high-calorie (approximately 800 to 1000 calories) meal is

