- Higher incidence of dose reduction and interruption occurred at 400 mg cohort was observed as compared to 200 mg and 300 mg cohort, which presumably led to lower clinical efficacy at the 400 mg cohort (ORR 25% at 400 mg). As the doses of 100 mg or above demonstrated clinical activity, and 200 mg or 300 mg is expected to overcome PK variability of DZD9008 to achieve pharmacological relevant exposure required from different subtypes of Exon20ins, thus selecting both 200 mg and 300 mg is appropriate to further evaluate DZD9008 dose optimization for the phase 2 pivotal study.
- DZD9008 elimination half-life is approximately 50 hours following a single dose across the doses investigated, which supports the once daily dosing regimen of DZD9008 in clinical development.

Ethnic sensitivity

 Based on the available data, no obvious difference in safety, PK and anti-tumor efficacy of DZD9008 was observed between Asian and White patients across different regions/countries. Therefore, Dizal believes that the use of same dose and schedule across different regions and countries is appropriate.

Patients enrolled to Part B will receive repeated dosing of DZD9008 at 200 mg or 300 mg once daily. Following review and approval form IEC/IRB and/or local regulatory authority (as applicable) on the optimal RP2D selction, eligible patients can be enrolled into the optimal RP2D cohort. The ongoing patients previously randomized to the suboptimal Part B dose cohort can maintain the same dose level, or shift to receive the optimal RP2D, if judged by the investigator that it is of the best clinical benefit to patients and re-consent is needed (see section 5.1). DZD9008 will be administrated with food as dosing with high fat food in Part A showed limited effect on DZD9008 exposure. Patients with prior therapy may be stratified into subcohorts when data is analyzed.

Patients will receive repeated daily dosing of DZD9008 until disease progression, intolerable AEs, discontinuation criteria have met or withdrawal of consent.

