Venous blood samples will be taken at the time points shown in Table 6. The date and time of dosing and collection of each sample will be recorded.

A 30 min window is allowed for pre-dose sampling. A 5 min window will be allowed for samples taken at 0.5 hour and 1 hour; a 10 min window for samples taken at 2 - 10 hour; an 1 hour window for samples taken at 12 hour and 24 hour, a 2 hour window at 48 hour, 72 hour, 120 hour and 168 hour (Table 6).

Time points on day1 and 9 are pre-dose, 0.5, 1, 2, 3, 4, 6, 8, 10, 12, 24, 48, 72, 120 and 168 hours post-dose (treatment time might be updated upon emerging human PK data).

Time point on Cycle 2 Day 1: pre-dose.

Date: July 24,2023

The timing for PK sampling may be adjusted with emerging data during the study, in order to ensure appropriate characterization of the plasma concentration-time profiles of DZD9008.

Blood samples (approximately 2 mL at each time point) will be collected and put into lavender top (EDTA) Vacutainer® evacuated collection tubes at the time points indicated.

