7.9.5 The effect of high fat meal

For the assessment of the effect of high fat meal, the primary PK variables $AUC_{(0-\infty)}$ and/or $AUC_{(0-t)}$ and/or $AUC_{(0-t)}$, and C_{max} of plasma DZD9008 will be analyzed in food effect analysis set. These parameters will be natural log-transformed and analyzed using a linear mixed effects model with fixed effects for sequence, period and treatment, and random effect for patient nested within sequence. The difference in treatment means will be determined along with its associated 90% CI and back-transformed to give an estimate of the effect of food on the exposure of DZD9008. The results of this analysis will be presented in terms of geometric means for both treatments, the effect of food on the exposure of DZD9008 (ie, the ratio of the treatment geometric means) and its 90% CI.

Date: July 24,2023

In the event of relevant carry-over exposure across periods (predose concentration exceeds 5% of C_{max} for DZD9008 in period 2), the primary analysis will be performed excluding the Period 2 data for patients meeting the carry-over criteria. A secondary statistical analysis may be performed including all patients, irrespective of the degreee of carry-over. If appropiorate, an exploratory analysis on carry-over adjusted concentrations and PK parameters may also be performed.

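### The food-effect schedule (second dose on Day 9, 192 h) contradicts the protocol's own wash-out rule (250 h at a 50-hour half-life), and following it could trigger the 5% carry-over exclusion in many patients

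*Protocol*

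**What the plan says.** **Wash-out rule.** Protocol 5.1.3: "After a 7-day washout period or 5 x half-lives (whichever is longer), these patients will be switched to receive a single dose" under the other meal condition. The note to Figure 2 adds: "The washout time of each treatment period might be updated in light of emerging human PK data".

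**Schedule.** Protocol 6.5.1.1 (food effect): "Time points on day1 and 9 are pre-dose, 0.5, 1, 2, 3, 4, 6, 8, 10, 12, 24, 48, 72, 120 and 168" hours post-dose. The same Day 9 appears in 6.3.3 (vital signs), 6.3.4 (laboratory tests), 6.3.5.1 (ECG) and Tables 6, 12 and 17. The text sections qualify it: "treatment time might be updated upon emerging human PK data". Tables 6 and 12 carry similar notes. Section 6.1 says that assessment schedules may change and that updated tables will be supplied outside the protocol.

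**Half-life.** Protocol 5.1.4: "DZD9008 elimination half-life is approximately 50 hours following a single dose across the doses investigated". Sections 2.3.5, 5.2.4 and 6.4.3.1 give the same figure.

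**Analysis.** Protocol 7.9.5 fits a mixed model with fixed effects for sequence, period and treatment and a random patient effect. Carry-over is relevant when the "predose concentration exceeds 5% of C_{max} for DZD9008 in period 2". In that case "the primary analysis will be performed excluding the Period 2 data for patients meeting the carry-over criteria". An analysis of all patients regardless of carry-over is optional, and so is an exploratory carry-over-adjusted analysis.

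**Status.** Section 2.3.5 reports that the high-fat meal has been evaluated in 12 patients of this study and in 20 healthy subjects of a separate study, with no to negligible effect in both.

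**The concern.** The current protocol states a half-life of about 50 h, yet every visit table and sampling section still gives a dosing day that falls short of the wash-out in 5.1.3. The shortfall matters because 7.9.5 attaches a consequence to it: patients over the 5% limit lose their period 2 data in the primary analysis. A crossover is used so that each patient acts as his or her own control, and each lost period 2 profile gives up that pairing. The loss is also selective. It falls on patients with longer half-lives and, because the limit is a fraction of Cmax, it depends on the exposure being measured. The effect of food on exposure is a stated secondary objective of Part A (1.1.1.2), and 5.1.4 cites the high-fat result when it explains dosing with food in Part B.

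**Working it through.** **Inputs from the documents.** Half-life about 50 h (5.1.4); dosing on Days 1 and 9 (6.5.1.1), so (9 − 1) × 24 = 192 h apart; wash-out is the larger of 7 days and 5 half-lives (5.1.3); limit 5% of Cmax (7.9.5); about 10 patients, 5 per sequence (5.1.3).

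**Assumed, not in the documents.** Shape of the concentration curve, between-patient spread of half-life, and within- and between-patient CV of exposure.

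**1. Schedule against rule.**
- Rule: max(168, 5 × 50) = 250 h = 10.4 days.
- Schedule: 192 h = 192/50 = 3.84 half-lives.
- Day 9 meets the rule only if the half-life is at most 192/5 = 38.4 h.

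**2. Residual in a typical patient.**
- Mono-exponential decline: 2^(−192/50) = 7.0% of Cmax, or 0.0698/1.0698 = 6.5% if the residual is counted in the period 2 Cmax.
- One-compartment oral model with absorption rate 2 to 0.2 per hour: 6.8–8.5% of the period 2 Cmax.
- At 250 h: 2^(−5) = 3.1%.
- With a distribution phase, the Day 9 residual is 7.0% times the terminal-phase intercept as a share of Cmax. It falls below 5% when that share is under 0.05/0.0698 = 72% (4.2% at a share of 60%, 3.5% at 50%).

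**3. Share of patients over 5% on Day 9.** Under mono-exponential decline a patient exceeds the limit if the half-life is above 192 × ln 2/ln 20 = 44.4 h (45.2 h if the residual is counted in Cmax). For a lognormal half-life, with s = √ln(1 + CV²):

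| Assumed CV | 50 h is the median | 50 h is the mean |
|---|---|---|
| 20% | 73% | 69% |
| 30% | 66% | 60% |
| 40% | 62% | 55% |
| 50% | 60% | 51% |

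The lowest value, 49%, comes from the 45.2 h threshold with CV 50% and 50 h as the mean.

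**4. Can the model still estimate the food effect?** Write the cell means as A1 = μ, A2 = μ + π + τ, B1 = μ + σ + τ, B2 = μ + σ + π, where σ is sequence, π period and τ food.
- If sequence B loses all its period 2 data, three cells remain for four fixed effects. They give only π + τ and σ + τ, so τ cannot be separated. The same holds for sequence A.
- With exceedance probability p and five patients per sequence, the chance that at least one sequence is emptied is 1 − (1 − p⁵)². This is 6% at p = 0.50, 15% at p = 0.60 and 37% at p = 0.73.
- With six per sequence, if the 12 reported patients were split evenly, the same formula with p⁶ gives 3% to 28%.

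**5. Precision when the model is estimable.** Assume within- and between-patient CVs of 25% and 50% and a true ratio of 1. The within-patient log-scale SD is √ln(1.0625) = 0.246.
- All 10 pairs: half-width 1.86 × 0.246 × √(2/10) = 0.205, so a 90% CI of 0.81–1.23.
- Two patients per sequence keep period 2 (6 of 10 excluded): the mixed model gives a standard error of 0.168. With 8 df the 90% CI is 0.73–1.37; crediting only 2 df, it is 0.61–1.63.

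**The case against.** The strongest reply is that Day 9 is provisional. Sections 5.1.3 and 6.5.1.1 and the notes to Tables 6 and 12 allow the timing to move, and 6.1 says updated tables may sit outside the protocol. A site that followed 5.1.3 would see a residual of about 3%, and the exclusion would rarely matter for a typical patient. This stands in part. A reader might infer that patients were dosed on Day 9; the documents do not show that, and section 2.3.5 gives neither the period 2 dosing day nor the number over 5%. The contradiction in the text remains.

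Three other stronger readings are tempting:
- *The primary analysis becomes five fed against five fasted patients.* Section 7.9.5 drops period 2 only for patients over the limit. Taking the median-based shares above, the chance that all 10 exceed it is p¹⁰, about 0.6–4%. In that event the stated model could not estimate the food effect at all, so a 5-versus-5 comparison is not the planned analysis.
- *Most patients will certainly exceed 5%.* This needs a half-life spread and a curve shape that the documents do not give. A marked distribution phase could make exceedance a minority outcome.
- *Dosing with food in Part B rests on an imprecise comparison.* Section 2.3.5 also cites the separate 20-subject study with the same conclusion, and gives gastrointestinal tolerability as a reason for taking the drug with food.

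The plan also already names an all-patient analysis and a carry-over-adjusted one. Both are optional, so neither is a safeguard as written.

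**Conclusion.** The contradiction is firm and needs only the protocol's figures: 192 h scheduled against 250 h required. The consequence is conditional on Day 9 being followed and on near mono-exponential decline. A typical pre-dose level is then about 7% of Cmax, and roughly half to three-quarters of patients lose period 2 in the primary analysis, given an assumed half-life CV of 20–50%. The chance that the stated model cannot estimate the food effect is then about 6–37% with five patients per sequence. Confidence is moderate, because the spread, the curve shape and the actual dosing days are not in the documents. The point is worth correcting, but it does not overturn the reported food-effect conclusion.

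**What to change.** 1. Reconcile Day 9 in 6.3.3, 6.3.4, 6.3.5.1, 6.5.1.1 and Tables 6, 12 and 17 with the wash-out rule in 5.1.3, given the half-life now stated. Which interval should apply is for the sponsor to settle.
2. In 7.9.5, change the all-patient analysis from *may* to *will* whenever any period 2 data are excluded, and name the carry-over-adjusted analysis as a further sensitivity analysis. Making the adjusted analysis primary is not proposed: the result has already been reported, so that would be a post-hoc change of primary method.
3. Report the actual period 2 dosing days, the number of patients over 5%, and whether the primary model was estimable after exclusions.

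The cost is text and table edits and slightly more analysis. The all-patient result will include some carry-over, and should be read beside the primary result with that in mind.

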6.5.1.2 Part A expansion

Blood samples

Venous blood samples will be taken at the time points shown in Table 7. Discussion with the Clinical Pharmacologist from Dizal Pharmaceuticals is required as to any impact if dose interruption occurs within 3 days of scheduled time points for PK sampling. The date and time of dosing and collection of each sample will be recorded.

Time points on Cycle 1 Day 1 and Cycle 2 Day 1 are pre-dose, 0.5, 1, 2, 3, 4, 6, 8, 10, 12, and 24 hour post-dose. On Cycle 1 Day 8 Day 15, and Cycle 3, 4 Day 1, pre-dose samples are collected (Table 7).

The timing for PK sampling may be adjusted with emerging data during the study, in order to ensure appropriate characterization of the plasma concentration-time profiles of DZD9008.

Blood samples (approximately 2 mL at each time point) will be collected and put into lavender top (EDTA) Vacutainer® evacuated collection tubes at the time points indicated.

6.5.1.3 Part B extension

Patients at selected sites will be invited for intense PK studies (approximately 10% - 30% of patients for each arm) and the remaining for sparse PK to characterize DZD9008 pharmacokinetics as shown in Table 8 and Table 9.

Throughout the treatment, the PK sampling time might be time-matched with the PRO-CTCAE assessments as described in Table 14. Beyond Cycle 3, the PK sampling time might be time-matched with efficacy assessment as described in section 6.8.1. Flexible sampling schedule will be implemented to improve the site feasibility. For example, if the patient already took the study drug before the on-site visit, the patient is still eligible for PK sample collections if the accurate dosing time and sample collection time are recorded accurately.

If there is a dose interruption, dose reduction, or an early termination due to an AE or there is an SAE, the investigator may choose to collect an unplanned blood sample (if possible) within the 24 hour after the last dose, which will be used to explore the exposure-response relationship between study drug exposure and AEs.

Table 5 Blood PK sampling schedule (Part A, dose escalation)

									Multi	ple dosing	
Time relative to dose	Single	dosing	(Part A	, Dose	escala		iple d Cycle		Multiple dosing Cycle 2	Multiple dosing Cycle 3, 4, 5	
	D1	D2	D3	D4	D6	D8	D1	D8	D15	D1	D1
Pre-dose	X						X	X	X	X	X
0.5 hour	X									X	
1 hour	X									X	
2 hours	X									X	
3 hours	X									X	
4 hours	X									X	
6 hours	X									X	
8 hours	X									X	
10 hours	X									X	
12 hours	X									X	
24 hours		X								X (D2, pre-dose)	
48 hours			X								
72 hours				X							
120 hours					X						
168 hours						X					

Note: The treatment date and sample collection time for each period might change upon emergent human PK data

- a. A 30 min window is allowed for pre-dose sampling.
- b. A 5 min window is allowed for samples taken at 0.5 hour and 1 hour;
- c. A 10 min window for samples taken at 2-10 hours;
- d. A 1 hour window for samples taken at 12 hours and 24 hours,
- e. A 2 hour window for samples taken at 48 hours, 72 hours, 120 hours and 168 hours.

Table 6 Blood PK sampling schedule (Part A, food effect)

Time		Period 1						Period 2					Cycle2
relative to dose	D1	D2	D3	D4	D6	D8	D9	D10	D11	D12	D14	D16	D1
Pre-dose	X						X						X

Time								Period 2					
relative to dose	D1	D2	D3	D4	D6	D8	D9	D10	D11	D12	D14	D16	D1
0.5 hour	X						X						
1 hour	X						X						
2 hours	X						X						
3 hours	X						X						
4 hours	X						X						
6 hours	X						X						
8 hours	X						X						
10 hours	X						X						
12 hours	X						X						
24 hours		X						X					
48 hours			X						X				
72 hours				X						X			
120 hours					X						X		
168 hours						X						X	

Note: The treatment date and sample collection time for each period might change upon emergent human PK data.

- a. A 30 min window is allowed for pre-dose sampling.
- b. A 5 min window is allowed for samples taken at 0.5 hour and 1 hour;
- c. A 10 min window for samples taken at 2-10 hours;
- d. A 1 hour window for samples taken at 12 hours and 24 hours,
- e. A 2 hour window for samples taken at 48 hours, 72 hours, 120 hours and 168 hours.

Table 7 Blood PK sampling schedule (Part A expansion)

Time relative		Cycle 1	Cycle 2	Cycle 3, 4	
to dose	D1	D8	D15	D1	D1
Pre-dose	X	X	X	X	X
0.5 hour	X			X	
1 hour	X			X	
2 hours	X			X	
3 hours	X			X	
4 hours	X			X	
6 hours	X			X	

Time relative		Cycle 1	Cycle 2	Cycle 3, 4	
to dose	D1	D8	D15	D1	D1
8 hours	X			X	
10 hours	X			X	
12 hours	X			X	
24 hours	X (prior to next dose)			X (prior to next dose)	

Note: The treatment date and sample collection time for each period might change upon emergent human PK data.

- a. A 30 min window is allowed for pre-dose sampling.
- b. A 5 min window is allowed for samples taken at 0.5 hour and 1 hour;
- c. A 10 min window for samples taken at 2-10 hours;
- d. A 1 hour window for samples taken at 12 hours and 24 hours.

 Table 8
 Blood collection for intense PK (Part B extension)

Time	Cy	Cycle 1			Cycle 3	Cycle 5	Cycle 7	Cycle 9	Cycle 11
relative to dose	D1	D8	D15	D1	D1	D1	D1	D1	D1
Pre-dose ^a	X	X	X	X	X	X	X	X	X
1 hour ^b	X				X				
2 hours ^c	X				X				
3 hours ^c	X				X				
4 hours ^c	X				X				
6 hours ^c	X				X				
8 hours ^c	X				X				
24 hours ^d	X (prior to next dose)				X (prior to next dose)				

- a. A 30 min window is allowed for pre-dose sampling.
- b. A ± 5 min window is allowed for samples taken at 1 hour;
- c. $A \pm 10$ min window for samples taken at 2-8 hours;
- d. A ± 1 hour window for samples taken at 24 hours.

Note: When the timing of a PK or safety laboratory blood sample coincides with the timing of ECG measurements, the ECG will be completed before the collection of the blood samples.

Date: July 24,2023

Table 9 Blood collection for sparse PK (Part B extension)

Time	Cycle 1		Cycle 2	Cycle 3	Cycle 5	Cycle 7	Cycle 9	Cycle 11	
relative to dose	D1	D8	D15	D1	D1	D1	D1	D1	D1
Pre-dose ^a	X	X	X	X	X	X	X	X	X
4 hours ^b	X				X				
8 hours ^b	X				X				

a. A 30 min window is allowed for pre-dose sampling.

Note: When the timing of a PK or safety laboratory blood sample coincides with the timing of ECG measurements, the ECG will be completed before the collection of the blood samples.

6.5.2 Determination of drug concentration in plasma and urine samples

Samples for determination of DZD9008 and/or metabolite DZ0753 concentrations in plasma will be analyzed using a validated bioanalytical method. All samples within the known stability of the analysts of interest at the time of receipt by the bioanalytical laboratory will be analyzed. Full details of the analytical method used will be described in a separate bioanalytical report.

In addition, the pharmacokinetic samples may be subjected to further analyses by Dizal or CROs in order to investigate the presence and/or identity of additional drug metabolites. Any results from such analyses will be reported separately from the Clinical Study Report.

Details on sample processing, handling, shipment and storage are provided in the Laboratory Manual.

6.5.3 Other parameters

A biomarker to determine CYP3A induction, the ratio of 4-β-hydroxy cholesterol / total cholesterol, will be measured at pre-dose of Cycle 0 Day 1, Cycle 1 Day 1, Day 8 and Day 15, Cycle 2 Day 1 (Part A Dose escalation only).

Blood samples (approximately 6 mL at each time point) will be collected and put into lavender top (EDTA) Vacutainer® evacuated collection tubes at the time points indicated.

6.6 Exploratory research

If a patient agrees to participate in the exploratory biomarker research, component of the study biological samples (e.g., blood, plasma, archived and study-obtained tumor, etc.) will be collected and may be analyzed for exploratory biomarkers to assess correlations with disease activity, effects of study drug and clinical outcomes.

The results of this exploratory biomarker research will be reported separately and will not form part of the Clinical Study Report.

The results of this exploratory biomarker research may be pooled with biomarker data from other studies with the study drug to generate hypotheses to be tested in future studies.

b. $A \pm 10$ min window for samples taken at 2-8 hours;

Date: July 24,2023

6.6.1 Exploratory analyses to support companion diagnostics development

In Part B, all patients will be asked to provide consent to mandatorily donate archived tumor samples (if more than one FFPE blocks from a patient, tissue from the most recent one is preferred) or any fresh tumor biopsies (if archived tumor sample is not available) for confirmation of EGFR Exon20ins status in Sponsor designated central laboratory

using the designated assay and for the development and approval of tissue-based companion diagnostics for DZD9008. If a pre-study written documentation of EGFR Exon20ins in tumor tissue is available from Sponsor designated central laboratory using the designated assay, no additional tumor sample needs to be submitted. The prior treatment must be clearly indicated for each archival tumor sample provided.

In Part B, the mutation test used in Sponsor designated central laboratory to select EGFR Exon20ins positive patients for this study will be developed for future approval as a companion diagnostics for DZD9008. Some residual tissue and/or DNA will be used for necessary technical studies for future companion diagnostics development and approval.

In addition, all patients in Part B will be asked to provide plasma samples at screening. These samples will be used for the extraction of circulating free tumor DNA (ctDNA) and assessing EGFR Exon20ins status for the development and approval of liquid biopsy companion diagnostics. The plasma samples may also be used for future exploratory research into factors that may influence development of DZD9008 in NSCLC or tumor response to DZD9008.

Details of sample collection, processing, shipping and storage will be described in the Laboratory Manual. For sampling schedule, see Study Plan (Table 14).

